218 significantly greater reductions in the number of binge episodes per week as compared to those
219 on placebo (n = 76).

220

221 *Of note, the final sample size is n=36 total.*

222

223 The trial has the following **secondary aims and hypotheses**.

224

225 **Aim 2.** We will compare the proportion of participants in the two groups who achieve remission
226 from binge eating at week 17, defined as having no binge episodes for the previous 4 weeks.

227

228 **H₂:** We hypothesize that significantly more participants in the liraglutide 3.0 mg/d group will
229 achieve remission at week 17 as compared to the placebo group.

230
231 **Aim 3.** We will compare differences between the liraglutide 3.0 mg/d and placebo groups in
232 changes in body weight, global improvement BED symptom improvement, cognitive restraint of
233 food intake, dietary disinhibition, perceived hunger, quality of life, and depressed mood at week
234 17.

235
236 **H₃:** We hypothesize that participants randomized to liraglutide 3.0 mg/d as compared to those
237 assigned to placebo, will lose significantly more weight, and show greater improvements in
238 investigator-rated global BED symptoms, cognitive restraint of food intake, dietary disinhibition,
239 hunger, quality of life, and depressed mood. (We note that these latter comparisons, Aims 2 and
240 3, are considered exploratory. The study is not powered to determine significant differences
241 among groups on these outcomes.)

242
243 *We note that the Eating Inventory subscales (restraint, disinhibition, and hunger) were*
244 *completed at baseline and treatment end only, and we may not have enough completers to run*
245 *the final analyses for this secondary outcome.*

246
247 **Endpoints:**

248
249 **Primary**

250
251 The primary endpoint is change in binge episodes per week from randomization (week 0) to
252 study end (week 17).

253
254 **Secondary**

255
256 The secondary endpoints include examining the proportion of participants who have achieved
257 remission from binge-eating (no binge episodes between weeks 13 – 17), week 17 rating on the
258 interviewer-based Clinical Global Impression of Improvement Scale (CGI-I)[24] for global
259 assessment of BED symptoms, and changes in body weight, cognitive restraint of food intake,
260 dietary disinhibition, perceived hunger, quality of life, and depressed mood.

261
262 *(See note above regarding restraint, disinhibition, and hunger variables.)*

263
264 **Study type:**

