535 contraindications to the use of liraglutide, as detailed in the inclusion/exclusion criteria.
536

537 **Run-In Period**

538 Upon successful completion of the screening visit, subjects will be asked to not change anything
539 and eat as they normally would for 2 weeks. Once per week over these two weeks they will
540 receive a brief survey through REDcap to assess their binge eating episodes. For those without
541 internet access, study staff will call the participant to ask this information over the phone. If
542 participants report having at least one binge episode per week (a total of two or more during the
543 two weeks), they will be included in the trial. Subjects will be trained at the screening visit on
544 general guidelines for the definition of a binge episode.

545
546

Table 1. Timeline and Procedures

	Screening		RCT									
	Weeks											
	Screen	2-week run-in	Randomization/ Week 0	1	3	5	7	9	11	13	15	17
Procedures												
Informed consent	x											
Adverse events actively collected	x	x	x	x	x	x	x	x	x	x	x	x
Behavioral evaluation	x											
History and physical	x											
EKG	x											
Blood draw	x											x
Labs	x											x
Log of BED behaviors		x										
Self-reported outcomes			x	x	x	x	x	x	x	x	x	x
Medical visit			x	x	x	x	x	x	x	x	x	x
Psychological assessment of BED symptoms	x		x	x	x	x	x	x	x	x	x	x
Vital signs	x	x	x	x	x	x	x	x	x	x	x	x

547
548
549
550

Note: Shaded weeks are formal assessment weeks. Data regarding binge episodes, weight, vital signs, mood and suicide risk, and other self-reported outcomes will be collected at each medication visit, as well.

551 **Randomization Visit**

552

553 Subjects who continue to meet eligibility criteria assessed at the screening visit and during the
554 run-in period will be scheduled for a randomization visit at the Center within 3 weeks of their
555 screening.

556

557 Subjects will be randomly assigned to the two interventions in equal numbers (i.e., 1:1 ratio).
558 This will be accomplished using a computer-generated algorithm operated by the Investigational
559 Drug Service of the University of Pennsylvania. Assignment will be made from randomly varied
560 block sizes (2, 4, or 6), realizing that this method may require slightly more than 152 participants
561 to be randomized in order to achieve perfect balance between the two groups.

562

563 The subject's weight, blood pressure, and pulse will then be measured, following the methods

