696 compound symmetry covariance structure (congruent with the primary analytic plan) with a total
697 of 10 assessment points and an ICC parameter equal to 0.59 (this is the value that was used as the
698 auto correlation rho in PASS), estimated based on data collected from similar populations within
699 our Center for Weight and Eating Disorders [46], i.e., reduction in nocturnal ingestions per week
700 among patients with night eating syndrome with an SSRI. There is often overlap between
701 persons with night eating syndrome and BED and we believe that the variance in improvements
702 from week to week in core symptoms of these disorders would be similar. Based on these
703 estimates, a baseline sample size of 152 participants (76 per group) with a 15% attrition rate
704 (actual total n=132) will give 80% power to detect a clinically relevant mean difference in degree
705 of reduction in binge episodes of 1.6 per week (effect size: 0.39) to be significant at alpha = 0.05,
706 based on a two-sided test. All secondary outcomes will be considered exploratory and evaluated
707 at the alpha=0.05 level. However, those exploratory analyses will provide valuable findings on
708 changes in weight and other clinically meaningful changes in eating disordered attitudes and
709 behaviors that have not been examined previously in relation to the use of liraglutide. The power
710 analysis was conducted using the PASS software, Version 11 NCSS LLC, Kaysville, UT [47].
711

712 **Statistical Methods**

713 Preliminary and descriptive analyses. All data will first be assessed for missing and out-of-range
714 values with basic statistical procedures such as univariate statistics (means, confidence intervals,
715 standard deviations, ranges, frequencies, proportions, percentiles) and graphs such as histograms,
716 box and whisker plots, scatter plots and Q-Q plots. All questions of data quality will be
717 investigated and resolved before any statistical modelling, as complete and accurate data are
718 essential for unbiased estimates and confidence intervals.
719

720 Baseline and demographic characteristics will be summarized overall for all subjects and by
721 treatment group. Means and confidence intervals will be provided for continuous variables and
722 frequencies and percentages for categorical variables. Graphical methods mentioned above will
723 be used to examine distributions and identify potential influential points. The balance of baseline

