724 measures across the two treatment groups will be compared using appropriate 2-sample tests,
725 including Wilcoxon rank-sum and t-tests for continuous variables, and Fisher's exact and Pearson
726 Chi-square tests for categorical variables. Any baseline variables found to be associated with
727 treatment condition will be added to the outcome analysis as a covariate.

728
729 **Primary analysis.** The primary outcome is the degree of reduction in binge episodes per week.
730 It is count data that is likely to be skewed, so a shifted log transformation will be considered to
731 stabilize the distribution to better meet the normality assumptions. To address the primary aim 1,
732 a mixed effects model will be fit with Treatment Group (liraglutide 3.0 mg/d and placebo) as a
733 between subjects factor and Time (Weeks 1 through 17) as a categorical within-subjects factor.
734 Time is treated as a categorical factor so that we can use the group-time interactions with the
735 time main effect to estimate and test intention-to-treat (ITT) treatment group differences at each
736 time point, with the 17-week time point as our primary ITT test. In fitting a mixed effects model
737 with maximum likelihood, a variance-covariance structure must be selected. We will begin by
738 assuming a compound symmetry structure, but also consider criteria such as the Akaike's
739 Information Criterion (AIC) for selecting the best form of the variance-covariance structure
740 using Residual Maximum Likelihood (REML) (e.g., Compound Symmetry, Toeplitz, first-order
741 autoregressive, and unstructured). Furthermore, we will include as baseline covariates those
742 variables that have been established to be associated with the outcome based on prior literature,
743 including sex and age. The results from the mixed model will be summarized by mean (SE)
744 change from baseline for each treatment group at each time point.
745

746 Given the above definition of the ITT tests under the mixed effects model, the main interest in
747 this study is the to the test of the primary hypotheses that participants randomized to liraglutide
748 3.0 mg/d (N=76) will show superior improvements from baseline to treatment end (week 17) in
749 the number of binge episodes per week as compared to those on placebo (N=76). The primary
750 hypothesis will be evaluated at the alpha = 0.05 level and all other contrasts and

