751 secondary/tertiary outcomes/hypotheses will be considered exploratory and those results will be
752 interpreted with caution at alpha equal to 0.05 level. Analyses will be conducted using the
753 statistical software package, SAS for Windows (SAS Institute, Inc., Cary, NC) [48].
754

755 As a sensitivity analysis, we will alternatively use a negative binomial distribution to model the
756 rate of binge eating episodes per week (taking into account the trial duration for individual
757 subjects) and will count r as a number of binge eating episodes. The binge eating episodes per
758 week ratio will be compared between the liraglutide and placebo groups.
759

760 *Of note, the analysis plan for the primary outcome variable will remain the same, but the final
761 sample size will be 36 instead of 152.*

762
763 **Analyses for Aim 2.** To assess differences among the two conditions in the percentage of
764 participants who were in remission (2 binary outcomes), generalized estimating equation (GEE)
765 models will be fit with the same between group, within group, and interaction terms as presented
766 above, as well as, any relevant baseline covariates. A binomial distribution will be specified
767 using a logit link function, and the unstructured covariance matrix will be considered to adjust
768 for the within subject clustering of repeated measures data. From the GEE models, odds ratios
769 and 95% confidence intervals will be computed to compare the treatment groups at each time
770 point.
771

772 *Of note, this analysis will also be completed as proposed with the reduced sample.*

773 **Analyses for Aim 3.** The mixed effects model approach described for the primary analysis will
774 also be utilized to compare changes in body weight, global BED symptom improvement,
775 cognitive restraint of food intake, dietary disinhibition, perceived hunger, quality of life, and
776 depressed mood between treatment groups. Changes in these outcomes will also be summarized
777 by mean(SE) for each treatment group at each time point. If violations in the normality
778 assumption are observed, log transformations, as well as alternative distributions such as Poisson
779 and Negative binomial will be considered.

780
781 *Of note, cognitive restraint, disinhibition, and hunger will only be available for completers, so it*
782 *is unlikely that this model can be run for these variables. The other variables in this aim were*

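### Primary analysis calls the reduction in binge episodes count data and may log it, without fixing the response variable, the shift constant or the reporting scale

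*Combined protocol and SAP*

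**What the plan says.** In Statistical Methods, the primary analysis paragraph opens: "The primary outcome is the degree of reduction in binge episodes per week". Its next sentence is "It is count data that is likely to be skewed, so a shifted log transformation will be considered to" bring the distribution closer to normality. The model has treatment group as a "between subjects factor and Time (Weeks 1 through 17) as a categorical within-subjects factor", and results are to be summarised as mean (SE) "change from baseline for each treatment group at each time point". Sex and age are named as covariates; the baseline binge count is not.

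The Endpoints section fits a change score: "The primary endpoint is change in binge episodes per week from randomization (week 0) to" week 17. The Sample Size Calculation works on the same untransformed scale, with 80% power for a difference in the degree "of reduction in binge episodes of 1.6 per week (effect size: 0.39) to be significant at alpha = 0.05".

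One other analysis bears on this: "As a sensitivity analysis, we will alternatively use a negative binomial distribution to model the" weekly rate of episodes, comparing the arms as a ratio.

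The plan gives no shift constant, no rule for choosing one, no criterion for deciding whether to transform, and no back-transformation.

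**The concern.** The weekly number of episodes is a count. The reduction from baseline is a difference between two counts, and it is negative for anyone who binges more often than at baseline. A log shift that suits a count (add a small constant so that zeros can be logged) does not suit a difference: the constant must be larger than the worst deterioration in the data, and beyond that bound it is a free choice.

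Two things are at stake. First, the primary p-value could depend on a constant chosen after the data are seen. Second, a difference in the log of a shifted reduction is neither a difference in episodes per week nor a rate ratio, so it cannot be read against the 1.6-episode target or against the mean change that the plan says it will report.

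**Working it through.** **1. The plan's own sample size.** Inputs from the Sample Size Calculation: SD 4.1, difference 1.6, 10 assessments, ICC 0.59, two-sided alpha 0.05, power 80%.

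n per arm = 2 × (4.1 × (1.960 + 0.842) / 1.6)² × [1 + 9 × 0.59]/10 = 103.08 × 0.631 = 65.04, so 66 per arm and 132 analysed. This matches the plan. It is a calculation on untransformed reductions and does not carry over to a log scale.

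**2. Are negative reductions to be expected?** Entry needs only that "participants report having at least one binge episode per week (a total of two or more during the" two-week run-in, so later counts can easily exceed baseline. A normal approximation gives P(reduction < 0) = Φ(−mean/SD):

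| Source | Mean reduction (SD) | P(negative) |
|---|---|---|
| Sibutramine trial, placebo arm (background section) | 2.0 (2.3) | 19% |
| Lisdexamfetamine trial, placebo arm (background section) | 3.3 (2.04) | 5% |
| Planning SD, assumed mean 2 | 2 (4.1) | 31% |
| Planning SD, assumed mean 4 | 4 (4.1) | 16% |

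At the planning SD, even with mean 4, the chance of at least one negative value among 36 is 1 − (1 − 0.165)³⁶ = 99.8%. A shift would be needed.

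**3. How much does the constant matter, with normal reductions?** Simulated two-sample t-tests at week 17, 18 per arm, difference 1.6, assumed placebo mean reduction 2.0, log(reduction − minimum + e):

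| SD | Untransformed | e = 0.01 | 0.1 | 0.5 | 1 | 5 | Significance changes across all e | 0.5 v 1 |
|---|---|---|---|---|---|---|---|---|
| 4.1 | 20% | 6% | 12% | 16% | 17% | 19% | 14% | 2% |
| 2.3 | 52% | 23% | 36% | 44% | 47% | 51% | 30% | 3% |

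As e grows, the result approaches the untransformed one.

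**4. The same question with count data.** Simulated gamma-Poisson counts, true rate ratio 0.5, several assumed dispersions, again at a single visit:

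- Shifts of 0.5 and 10 above the minimum disagree on significance in 7–8% of trials at 18 per arm and 9–11% at 66 per arm.
- Shifts of 0.5 and 1 disagree in 1–3%.

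Power at 18 per arm:

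| Analysis | Power |
|---|---|
| Raw reduction | about 19% |
| Shifted log of the reduction | 17–21% |
| Raw count, adjusted for baseline count | 34–44% |
| log(count+1), adjusted for baseline log(count+1) | 41–48% |

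Logging the reduction buys essentially nothing at this size. Most of the gain in the last two rows comes from adjusting for baseline; the log of the count adds a little more.

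**5. One constructed dataset of 36, as illustration only.** With the shift set at 1 minus the minimum, moving the worst patient in the active arm from −5 to −10 raised the shift from 6 to 11 and moved the log-scale p-value from 0.05 to 0.51. The untransformed p-value moved from 0.002 to 0.02.

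**The case against.** The strongest reply is that the authors mean the weekly count. Those words fit the number of episodes, and the primary hypothesis is phrased as improvement in that number. The sample size assumes ten assessments, and the ten visits (weeks 0, 1, 3, 5, 7, 9, 11, 13, 15 and 17) include week 0, which suits the count as response with change from baseline as a model contrast. Against this, the outcome is named as the reduction, the time factor starts at week 1, and results are reported as change. The text supports both readings, so a reader cannot tell which variable would be logged.

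Four stronger inferences are tempting, and the documents or the calculations do not support them.

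- *The log is settled.* It is only to be considered, so any dependence on the constant is conditional.
- *The worst patient fixes the constant.* The largest worsening sets a lower bound only; a generous constant brings the result close to the untransformed one.
- *The transformation fails to repair the skew.* In simulated counts at 18 per arm, median within-arm skew of the raw reduction was 1.1 to 1.5. After the log it was −0.5 to −0.7 with 1 above the minimum, 0.3 to 0.4 with 5, and 0.6 to 0.7 with 10. Only 0.5 overshot badly (−0.9 to −1.3).
- *Logging the reduction costs power.* At the very small constants in step 3 it does. At 0.5 and 10 with count data, power is about equal to raw at 18 per arm. In one setting at 66 per arm (baseline 4 per week, control at 55% of baseline) it was somewhat higher: 66–68% against 60%.

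Dependence on a constant is also not peculiar to the reduction. In simulated counts at 18 per arm, log(weekly count + c) with c from 0.1 to 1 changed significance in 8–9% of trials, against 17–23% for the shifted reduction with e from 0.01 to 5. The ranges differ, so this is not like for like. The difference in kind is that a count needs no shift derived from the data.

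The negative binomial analysis would help expose a result driven by the constant. That stands, but it is a sensitivity analysis and cannot settle the primary test.

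**Conclusion.** The point holds as a gap in specification with a concrete consequence. The plan calls a difference count data and leaves open which variable would be logged, with what constant, by what rule, and on what scale the effect would be reported. If the reduction is logged, the choice between widely spaced constants (0.5 v 10) changes significance in roughly 7–11% of trials; between neighbouring ones (0.5 v 1) in 1–3%. This is a modest risk, not evidence that the primary result is invalid.

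The percentages are illustrative. They rest on assumed dispersions and placebo means, and absolute power moves with the dispersion. They use single-visit tests in place of the repeated-measures model, with 18 per arm observed at week 17. The May 2019 note counts 5 completers and 10 participants still active, so week-17 data will be fewer than that.

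**What to change.** Amend the primary analysis paragraph to state:

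- The response is the weekly binge count at each post-randomisation visit, not the reduction.
- If a log is used, it is log(count+1), with the constant fixed at 1 in advance.
- The baseline count enters as a covariate on the same scale as the response, alongside sex and age. This supplies most of the power gain: at 18 per arm, from about 19% to 34–44% on the raw scale, or 41–48% with log(count+1), under the assumed dispersions.
- The choice between raw and log is made and recorded on pooled blinded data. Breaking of Blinded Codes already leaves a point for this, after the data are declared clean and before codes are released. The missing-data paragraph already promises pre-specification before unblinding for its own sensitivity analyses.
- The untransformed difference in episodes per week at week 17, with its confidence interval, is reported beside any ratio, so that it can be read against 1.6.

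Keep the negative binomial analysis as it is. The cost is SAP wording; no new data are needed. The small downside is that a log-scale effect is a ratio (here of count plus one), so both scales have to be shown and explained.

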660 Diagnostics.) Each blood draw will require approximately 1 tablespoon (i.e., 15 mls) of blood.
661 Blood pressure and pulse will be measured on each occasion using an automated monitor
662 (Dinamap, model 9300). Two readings will be taken on each occasion (at 1-minute intervals),
663 after participants have been seated for at least 5 minutes.

664

665 At baseline screening, participants will complete a history and physical examination and have an
666 EKG. Interpretation of results will use the categories "normal", "abnormal", not clinically
667 significant" or "abnormal, clinically significant". Subjects will be screened extensively (by a
668 physician or nurse practitioner) to determine that they have no contraindications to the use of
669 liraglutide or to possible weight loss.

670

671 **Other Assessments**

672 n/a

673

674 **Subject Compliance**

675 Subjects will be instructed to keep a medication diary to be reviewed at each visit, and they will
676 be asked if they have missed any doses since their last visit. We will also measure subjects'
677 medication adherence using injection counts from visual inspection of the dose counter taken
678 from subjects' injection pens. Subjects will be instructed to bring the pen to each session, and we
679 will record missed doses and problem solve with subjects if they are missing doses.

680

681

682 **Assessing Adverse Events**
683 All information regarding adverse events will be actively collected from the point of the first
684 study-related activity (i.e., completion of the informed consent procedure), through to each
685 participant's study endpoint. This includes adverse events that may be related to any study
686 procedure (i.e., laboratory tests or ECGs) that may not have been performed during normal
687 management of the participant, in addition to his/her use of liraglutide.
688

689 **STATISTICAL CONSIDERATIONS:**

690 **Sample Size Calculation**

691 A power analysis was conducted for the primary outcome, reduction in binge episodes per week
692 (i.e., last 7 days). Estimated variances and clinically relevant treatment differences were derived
693 from the literature using previous randomized controlled trials for BED [14, 45]. The common
694 standard deviation used was 4.1 [45], and the clinically relevant change in binge episode used
695 was 1.6 binge episodes per week [45]. Furthermore, a mixed effects model design assuming a

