783 *administered at each visit and can be included in the proposed models.*

784
785 **Safety analysis.** Given the modest sample size, we will not perform safety analysis. Instead,
786 safety labs will be reviewed on an individual basis with participants to assure that they are within
787 normal limits, and these will be available in summary for publications/presentations. The details
788 for reporting SAEs to the IRB and procedures for taking action to safeguard participants are
789 described in the safety monitoring plan.

790
791 **Missing data and statistical models.** Every effort will be made to obtain follow-up data on all
792 participants randomized. Based on prior studies that we have conducted, the dropout rate by 17
793 weeks could be as high as 15%. Our maximum likelihood approach assumes that any missing
794 outcome data are missing at random (i.e., missing data, including those due to drop-out, but not
795 dependent on any previously observed outcomes or treatment assignment). With this approach,
796 we will use all data that have been collected, without regard to whether data are missing for a
797 participant at another visit, including drop-out, and without explicit imputation of missing data.
798 We will conduct sensitivity analyses to examine the impact of missing data. Details regarding
799 the sensitivity analyses will be pre-specified prior to unblinding. Furthermore, we will assess
800 whether dropout status or level of compliance is associated with treatment condition as well as
801 baseline demographic variables using appropriate 2-sample tests, including Wilcoxon rank-sum
802 and t-tests for continuous variables, and Fisher's exact and Pearson Chi-square tests for
803 categorical variables, and all findings will be reported.

804
805 Change in frequency of binge episodes per week also will be analyzed using a per protocol
806 analysis that, for liraglutide-treated participants, includes only those who were able to tolerate
807 and adhered to the full dose of liraglutide 3.0 mg.

808
809 **Interim Analysis**

810 No interim analyses are planned (in order to maintain full power for the end-of-study
811 comparisons).

812
813 **Explorative Statistical Analysis for Pharmacogenetics and Biomarkers**

814 No explorative statistical analysis for pharmacogenetics and biomarkers will be performed.

815
816 *5.20.19 Of note, due to unforeseen low response to advertising and the mis-allocation of*

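### Remission (Aim 2) is analysed by GEE, but the plan's only missing-data argument is for maximum likelihood, so dropout tied to bingeing differently in the two arms would bias the week-17 odds ratio

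*Combined protocol and SAP*

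**What the plan says.** **Method for remission (Analyses for Aim 2).** The text reads "participants who were in remission (2 binary outcomes), generalized estimating equation (GEE". The model has a binomial distribution and logit link, the same group, time and interaction terms as the primary model, and an unstructured covariance that is to be considered. Odds ratios are reported at each time point. No weighting or imputation is named. A note keeps this analysis unchanged for the smaller sample.

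**Missing data (Missing data and statistical models).** Dropout by 17 "weeks could be as high as 15%. Our maximum likelihood approach assumes that any missing" outcome data are missing at random. The bracketed explanation is that missingness does not depend on earlier observed outcomes or on arm. All collected data are used, whether or not data are missing for a "participant at another visit, including drop-out, and without explicit imputation of missing data". The paragraph mentions neither GEE nor remission. It promises missing-data sensitivity analyses, to be detailed before unblinding, without naming a method or an outcome. Dropout will be compared with treatment condition and baseline demographics. Earlier bingeing is not on that list.

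**Outcome and visits.** Under Endpoints, remission means no binge episode between weeks 13 and 17. Visits fall at weeks 13, 15 and 17, and each interview covers the time since the last visit (Assessments for Efficacy).

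**Status.** Sample Size Calculation states that the test is "based on a two-sided test. All secondary outcomes will be considered exploratory and evaluated" at the 0.05 level, and the hypotheses section adds that Aims 2 and 3 are not powered.

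**The concern.** A mixed model fitted by maximum likelihood can tolerate dropout that depends on outcomes already observed, provided the model is right. GEE solves estimating equations rather than maximising a likelihood. Without weights or imputation it is not generally valid under that kind of dropout. The missing-data paragraph therefore covers the mixed models of Aims 1 and 3 and leaves Aim 2 without an argument.

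A participant who leaves while still bingeing drops out of the week-17 remission comparison. If that happens mainly in one arm, the odds ratio describes those who stayed and no longer compares the randomised groups. It could move in either direction: placebo remission would look too high if placebo participants left because they still binged, and the reverse pattern would flatter the drug.

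**Working it through.** **Step 1. The plan's own figure.** The documents give no figure for remission. The primary-outcome sample size does reproduce, and it supplies the planned arm size used under the objection. Inputs from Sample Size Calculation: "standard deviation used was 4.1 [45], and the clinically relevant change in binge episode used" and "was 1.6 binge episodes per week [45", ten assessments, correlation 0.59, two-sided 0.05, 80% power.
- Variance of the mean of ten measures: 4.1² × (1 + 9 × 0.59)/10 = 16.81 × 0.631 = 10.61.
- n per arm = 2 × (1.960 + 0.842)² × 10.61/1.6² = about 65, or 66 with the t correction. The total is 132 with power 80.6%, matching "actual total n=132) will give 80% power to detect a clinically relevant mean difference in degree".

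**Step 2. Two readings of the missing-data assumption.**
- If missing at random is meant, GEE as described is not covered.
- If the bracketed explanation is meant, GEE would be valid. The planned dropout comparisons would not test the key part of that assumption, because they omit earlier bingeing.

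**Step 3. How much is missing, and why** (note dated 5.20.19).
- Year 1: 5 + 1 + 9 + 4 + 2 = 21. Current year: 1 + 4 + 10 = 15. Total 36.
- On assigned treatment at week 17: at most 1 + 4 + 10 = 15.
- The other 36 − 15 = 21 split into 9 + 4 + 2 = 15 affected by misallocation and 5 + 1 = 6 ordinary dropouts.
- Ordinary dropout is 6/36 = 17%, or 6/(36 − 15) = 29% of those not misallocated. Ten were still active, so it could rise.

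**Step 4. Size of the bias, count model (assumed).** Poisson-gamma counts over nine visits, 5,000 per arm. The log-odds of placebo dropout rise by 0.25 per episode at the previous visit (capped at 8). Liraglutide dropout is unrelated to bingeing. Four-week remission is fitted at the last five visits with an unstructured working matrix.

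| Missing at week 17 | True OR | GEE | Multiple imputation |
|---|---|---|---|
| 11–15% | 1.70 | 1.59 | 1.67 |
| 23–26% | 1.65 | 1.42 | 1.61 |
| 53–57% | 1.58 | 1.09 | 1.56 |

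On the log scale, ln(1.70/1.59) = 0.07, or 13% of ln 1.70 = 0.53, and ln(1.65/1.42) = 0.15, or 30% of ln 1.65 = 0.50. With the same dropout mechanism in both arms the two figures were 1.72 and 1.71.

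**Step 5. A different model (assumed).** Latent-normal outcomes at five visits, correlation 0.8, 3,000 per arm. Remission rates are borrowed from the background text: A is 58.7% vs 42.8%, B is 50% vs 42%. IPW is GEE weighted by the true inverse dropout probabilities. Monte Carlo error is roughly 5%.

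| Rates, dropout, pattern | Full data | Independence GEE | Unstructured GEE | IPW |
|---|---|---|---|---|
| A, 15%, placebo only | 1.99 | 1.64 | 1.92 | 1.99 |
| A, 30%, placebo only | 1.99 | 1.23 | 1.64 | 1.91 |
| B, 15%, placebo only | 1.46 | 1.17 | 1.34 | 1.44 |
| B, 30%, placebo only | 1.46 | 0.88 | 1.21 | 1.43 |
| A, 30%, same in both arms | 1.99 | 2.28 | 2.10 | 1.98 |
| B, 30%, same in both arms | 1.46 | 1.61 | 1.54 | 1.50 |

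The direction agrees with step 4. An unstructured matrix removes part of the bias in large samples.

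**Step 6. Behaviour at the actual size.**
- With 36 participants and 15 reaching week 17, an unstructured GEE converged with a positive-definite matrix in 17 of 40 runs with five visits and 0 of 40 with seven. With complete data it did so in 40 of 40.
- At 18 per arm with arm-specific dropout and 23–30% missing, the true risk difference was 0.085. Observed data gave 0.050 and multiple imputation 0.077, with root mean squared error no worse.
- Scoring known non-remission without imputing the rest gave 0.047, so that rule alone does not remove the bias.

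**The case against.** **The bias needs dropout that differs by arm.** This stands. The documents expect gastrointestinal symptoms on the drug, which makes differing reasons for leaving plausible, but they do not show it.

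**A reader might infer that the remission effect could be erased or reversed.** The documents do not support that. No step 4 scenario with a true drug effect reversed. At the planned 15%, suppose every placebo dropout were a non-remitter and liraglutide dropout were random. Placebo remission among stayers under rates A would be 0.428/0.85 = 0.504, and the odds ratio would fall from 1.90 to 1.40. Under rates B it would fall from 1.38 to 1.02. In step 5, one-sided dropout reversed the odds ratio only under rates B at 30%, with independence working correlation, which is not the structure the plan names.

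**A reader might also take 21 of 36 (58%) as outcome-driven dropout.** Fifteen of those 21 come from misallocation, which nothing links to bingeing, so the 53–57% row is not the fair headline. The documents do not say that misallocated participants lack week-17 assessments. Being on assigned treatment is my criterion.

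**The bias is small against the noise.** This is true at the final size. With 7 and 8 observed and remission of 43% and 54% (assumed), SE(log OR) = √[1/(7 × 0.43 × 0.57) + 1/(8 × 0.54 × 0.46)] = 1.04. A bias of 0.15 is then 0.14 SE. At the planned 66 per arm the SE is 0.35, and a bias of 0.07 is about 0.2 SE.

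**Some of this is read from silence.** That the GEE is unweighted is an inference. The plan also does not say that someone with a binge recorded at week 15 and no week-17 visit counts as missing. The remission definition already allows that person to be scored as not remitted, but no rule says so.

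**Aim 2 is exploratory and sensitivity analyses are promised.** Both are true. They lower the priority, but no method for remission is yet specified.

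**Conclusion.** The point holds in a limited form. Aim 2 has no stated missing-data method of its own, the argument given for maximum likelihood does not extend to GEE, and the label and explanation of the assumption conflict. If dropout depends on earlier bingeing differently by arm, the illustrations show an attenuation of about 1.65 to 1.42 at roughly 25% missing and 1.70 to 1.59 at 11–15% missing. Documented ordinary dropout is 17% or 29%, depending on the denominator. If the mechanism is the same in both arms the bias is small and, in step 5 at 30% dropout, upward.

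These sizes rest on assumed dropout mechanisms, correlations and remission rates, not on trial data. With Aim 2 exploratory and intervals wide at n = 36, this should be corrected before unblinding, at modest priority.

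**What to change.** Before unblinding, amend the SAP as follows.

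1. State the assumption for Aim 2 as missing at random given the observed visit counts, and reconcile the label and its explanation in the missing-data paragraph.
2. Multiply impute missing visit counts with a simple model (arm, week-0 frequency, earlier visits), derive week-17 remission in each imputed set, compare the arms and pool.
3. Within that imputation, score as not in remission anyone with a binge already recorded in weeks 13–17. Do not use this rule on its own.
4. Keep the observed-data GEE as a secondary display, and name a simpler fallback working correlation for when the unstructured one cannot be estimated.
5. Add an analysis that counts missing as not remitted, as a sensitivity analysis.

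The cost is SAP wording and a short imputation program on counts already collected. The downside is that with 36 participants the imputation model must stay simple and the intervals will be wide.
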